### **9.3. Clinical Laboratory Tests**

#### **9.3.1. Laboratory Value Definitions**

All laboratory assessments will be performed using a central laboratory except for urine pregnancy tests (as applicable). Laboratory values and change from baseline values will be summarized descriptively by visit, and non-numeric test values will be tabulated when necessary.

Baseline will be determined according to Section 4.1.3. If there are multiple values that meet the criteria for baseline, the value from the central laboratory has priority over the value from the local laboratory. Thereafter, additional rules may be provided after consultation with the medical monitor to delineate which value will be defined as baseline.

#### **9.3.2. Laboratory Value Summaries**

Clinical laboratory tests, including hematology and serum chemistry, will be performed at the Protocol-specified visits. If specific safety issues arise, additional unscheduled laboratory tests/analyses may be performed at the discretion of the investigator.

All test results and associated normal ranges from central laboratories will be reported in SI units. All tests with numeric values will have a unique unit per test. Any laboratory test results and associated normal ranges from local laboratories will be converted to SI units.

When there are multiple laboratory nonmissing values for a participant's particular test within a visit window, the laboratory value with the smallest laboratory sequence number will be used in by-visit summaries.

For test results that will be summarized with available normal ranges, the number and percentage of participants with laboratory values being low, normal, high, and both low and high will be calculated for each test. This shift summary will be produced for each test for the FAS population in the CT period, as well as the LTS period for the LTS-EV population. Shift tables will be presented showing the change in CTCAE grade from baseline to worst grade postbaseline as well. The denominator for the percentage calculation will use the number of participants in the baseline category.

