6.5.1. Criteria and Procedures for Interruptions of Study Cream

Safety concerns should be discussed with the medical monitor immediately upon occurrence or awareness to determine whether the participant should continue or discontinue study cream.

In some circumstances, it may be necessary to temporarily interrupt treatment as a result of AEs or laboratory abnormalities that may have an unclear relationship to study cream. In the event that an AE is present only at a specific site of study cream application, treatment may be

temporarily withheld only at that lesional site and continued elsewhere. This should be recorded as a dose interruption on the AE eCRF page. Except in cases of emergency, it is recommended that any findings of concern (eg, AE) be confirmed and that the investigator consult with the medical monitor before interrupting study cream applications. Additionally, the investigator must obtain approval from the medical monitor before restarting study cream. Participants who experience a recurrence of the initial AEs upon restarting the study cream may need to permanently discontinue treatment with the study cream.

Participants should be closely monitored for the development of signs and symptoms of infection during treatment with the study cream and up to the safety follow-up visit. Study cream should be interrupted if a participant develops a serious infection, an opportunistic infection, or sepsis. Study cream application should not be resumed until the infection is controlled.

Instructions for interruption of study cream—related laboratory abnormalities are outlined in Table 7.

Table 7: Guidelines for Interruption and Restarting of Study Cream Due to Laboratory Abnormalities

AE Related to Study Cream	Action Taken
Any Grade 3 laboratory abnormality	Laboratory abnormalities should be confirmed with repeat testing within 48 hours whenever possible and immediate delivery of the laboratory results requested.
	• Interrupt study cream, based on clinical judgment in consultation with the medical monitor (whenever possible), taking into account the relatedness of the AE to the study cream and the participant's underlying condition.
	• Interruption may occur after the initial test result or may be delayed until or unless the repeat test confirms the laboratory abnormality; however, if the repeat test does confirm the laboratory abnormality, the study cream must be interrupted unless the medical monitor approves continuation.

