8.6. Unscheduled Visits

Unscheduled study visits may occur at any time medically warranted, including when participants develop new areas of AD (see Section 6.1). Any assessments performed at those visits should be recorded in the eCRF.

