#### **4.1.3. Baseline Value**

Baseline is the last nonmissing measurement obtained before the first application of ruxolitinib cream, unless otherwise defined.

When scheduled assessments and unscheduled assessments occur on the same day and the time of the assessment or time of first application is not available, use the following convention to determine baseline:

- If both a scheduled and an unscheduled visit are available on the day of the first application and the time is missing, use the scheduled assessment as baseline.
- If all scheduled assessments are missing on the day of the first application and an unscheduled assessment is available, use the unscheduled assessment as baseline.

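### By-visit laboratory summaries select on sequence number alone, so an earlier unscheduled draw in the same window could replace the scheduled value (minor)

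*SAP*

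**What the plan says.** SAP 9.3.2 sets the selection rule. Its condition is "When there are multiple laboratory nonmissing values for a participant's particular test within a visit window", and its choice is that "the laboratory value with the smallest laboratory sequence number will be used in by-visit summaries". No other criterion is given: not visit type, not distance from the target day, not laboratory.

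The same section expects extra draws: "If specific safety issues arise, additional unscheduled laboratory tests/analyses may be performed at the discretion of the investigator". Protocol 8.6 agrees: "Unscheduled study visits may occur at any time medically warranted, including when participants develop new areas of AD". Protocol Table 4 gives unscheduled visits their own column and marks serum chemistry and hematology in it.

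The SAP defines neither the visit window nor how the sequence number is assigned. SAP 4.1 covers Day 1, study day, baseline and partial dates only. The Protocol gives visit ranges of ± 3 days in the continuous treatment period and ± 7 days in the long-term safety period, but the SAP does not adopt them as analysis windows.

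Two neighboring sections do state a priority. SAP 9.3.1 puts central over local results when several values qualify as baseline. SAP 9.4 summarizes vital signs at scheduled visits.

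**The concern.** A record number says nothing about which draw represents the visit. Unscheduled laboratory tests are often done because something has happened to the participant. If such a result is chosen over the scheduled one, the by-visit mean mixes values taken at the nominal time with values taken because of an event, and the scheduled value drops out of the summary.

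The outputs at stake are the by-visit laboratory tables (3.3.1 and 3.3.2) and the mean plots of values, change and percentage change (Figures 4.5.1 to 4.6.3). Change in laboratory data is a secondary endpoint. If the exploratory comparison of hematology with trough concentration in Protocol 10.4.5 draws on the same by-visit values, a displaced result would also not come from the visit at which the PK sample was taken, because Table 4 schedules no PK sample at unscheduled visits.

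Reproducibility is also at stake. With the window and the sequence number undefined, two programmers could build different by-visit tables from the same data.

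**Working it through.** **The plan's own figure.** Protocol 10.1 gives the study's only design figure: more than a 99% chance of seeing at least one adverse event of interest with 100 participants and a 5% rate. It reproduces: 1 − 0.95^100 = 0.9941. The present point does not depend on it.

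**When the rule displaces a scheduled value.** Two undefined terms decide this.

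| Window | Sequence number | Extra draw before the scheduled one | Extra draw after it |
|---|---|---|---|
| By date | Chronological | Replaces the scheduled value | Scheduled value kept |
| By date | Not chronological | Depends on numbering | Depends on numbering |
| By visit label, unscheduled kept apart | Any | No competition | No competition |

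The clear problem is the first row, left-hand case. The right-hand case covers the repeats in Protocol Table 7 ("Laboratory abnormalities should be confirmed with repeat testing within 48 hours whenever possible") when the value being confirmed came from the scheduled draw. Protocol 8.3.5 also asks for results judged clinically significant to be re-tested until they settle. If windows are contiguous, a late re-test of this kind can fall in the next visit's window ahead of its scheduled draw.

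**Size.** The documents give no frequency of in-window extra draws and no size of shift, so these inputs are assumptions:
- p, the share of participants at a visit whose scheduled value is displaced: 1% to 5%.
- d, the difference between the displacing and the scheduled value: 1 to 2 SD, all in one direction.
- n, participants with a value at the visit: 80 to 100. The 100 is the planned enrollment in Protocol 10.1; the 80 is an assumed lower figure.

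Formulas, in SD units of the quantity summarized: mean shift = p × d; standard error = 1/√n, which is 1/√80 = 0.112 and 1/√100 = 0.100.

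| p | d (SD) | Mean shift (SD) | Shift / SE, n = 80 | Shift / SE, n = 100 |
|---|---|---|---|---|
| 1% | 1 | 0.01 | 0.09 | 0.10 |
| 1% | 2 | 0.02 | 0.18 | 0.20 |
| 3% | 1 | 0.03 | 0.27 | 0.30 |
| 3% | 2 | 0.06 | 0.54 | 0.60 |
| 5% | 1 | 0.05 | 0.45 | 0.50 |
| 5% | 2 | 0.10 | 0.89 | 1.00 |

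**How many extra draws this takes.** After Week 12, visits are 8 weeks (56 days) apart. Assume extra draws are spread evenly over that interval, at most one per participant.
- With a ± 7-day window, 7 of 56 days lie in the window before the scheduled draw (7/56 = 0.125). Displacing 5% needs 0.05/0.125 = 40% of participants to have an extra draw in the interval; displacing 1% needs 0.01/0.125 = 8%.
- With contiguous windows split at the midpoint, 28 of 56 days lie before it (0.5). Displacing 5% needs 0.05/0.5 = 10%; displacing 1% needs 0.01/0.5 = 2%.

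The upper end of the size table is therefore plausible only with wide windows or frequent extra draws.

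**What the rule does not touch.** Its wording is limited to by-visit summaries. The shift tables (3.3.3.1 to 3.3.6.2) go to the worst post-baseline value. The adverse event tables, including the events of interest, and Listings 2.8.1 to 2.8.4 do not use the selection.

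**The case against.** The case for leaving the rule alone is reasonable. The rule is prespecified and deterministic. With chronological numbering it keeps the scheduled value against any later confirmatory repeat. If unscheduled draws are kept under their own visit label, they may never compete at all. The study has one group and tests no hypotheses, and the outputs that would reveal laboratory harm do not pass through this rule. All of this stands, and it limits the point to a minor one. It does not remove it, because nothing in the SAP gives the scheduled draw priority after baseline, and a rule for several values in a window matters mainly when extra draws compete.

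Three stronger readings are tempting, and the documents do not support them.

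- A reader might infer that 9.3.2 departs from a general preference for scheduled values in SAP 4.1.3. There is none. The general rule is "Baseline is the last nonmissing measurement obtained before the first application of ruxolitinib cream, unless otherwise defined", whatever the visit type, so an unscheduled pre-treatment repeat can also replace a scheduled screening value. The scheduled preference applies only when both assessments fall on the day of first application and "the time is missing, use the scheduled assessment as baseline".
- A reader might infer that displacement is certain. It needs windows that capture unscheduled draws and numbering that puts the unscheduled draw first, and the SAP states neither.
- A reader might infer a bias in a known direction. Protocol 8.6 names new areas of AD as one reason for an unscheduled visit, and nothing says such visits shift hematology or chemistry. The same-direction shift above is an assumption made to bound the effect.

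**Conclusion.** The point holds in a limited form. SAP 9.3.2 selects by-visit laboratory values on sequence number, with no priority for the scheduled draw, proximity to the target day, or the central laboratory. If windows are date-based and numbering is chronological, an unscheduled draw that precedes the scheduled one in its window takes its place in Tables 3.3.1 and 3.3.2 and Figures 4.5.1 to 4.6.3.

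Under the assumed inputs the by-visit mean moves by 0.01 to 0.10 SD, at most about one standard error. The true size cannot be computed from the documents. No conclusion about rare or severe laboratory abnormalities rests on these summaries. Severity is minor; the reason to act is that a better rule is available at little cost.

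**What to change.** Amend SAP 9.3.2 as follows:

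1. Define the analysis window for each visit and state how the laboratory sequence number is assigned.
2. For by-visit summaries, use the scheduled-visit value, with central over local as in 9.3.1.
3. If the scheduled value is missing, use the value closest to the target day, with ties going to the earlier sample.
4. Keep the smallest sequence number only as the last tie-break.

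The worst-grade shift tables and listings need no change. The cost is a few sentences in the SAP and a small change to the derivation program; no extra data are needed.

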#### **9.4. Vital Signs**

Values at each scheduled visit, change, and percentage change from baseline for vital signs, including systolic blood pressure, diastolic blood pressure, pulse, temperature, and respiratory rate will be summarized descriptively. Height and weight values at each scheduled visit, change, and percentage change from baseline for height and weight will be summarized descriptively.

Criteria for clinically notable vital sign abnormalities are defined in [Table 4](#) and [Table 5](#). The abnormal values for participants exhibiting clinically notable vital sign abnormalities will be listed by age group. Alert vital signs are defined as an absolute value outside the defined normal range and percentage change greater than 25%. The abnormal values for participants exhibiting alert vital sign abnormalities will be listed.

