1. PROTOCOL SUMMARY

Protocol Title: A Phase 3, Open-Label, One-Year Safety Study of Ruxolitinib Cream in

Adolescents (Ages ≥ 12 Years to < 18 Years) With Atopic Dermatitis

Protocol Number: INCB 18424-315

Objectives and Endpoints:

Table 1 presents the primary and secondary objectives and endpoints.

Table 1: Primary and Secondary Objectives and Endpoints

Objectives	Endpoints		
Primary			
To evaluate the long-term safety and tolerability of ruxolitinib cream in adolescents with AD.	Incidence of TEAEs, assessed by monitoring the type, frequency, and severity of AEs.		
Secondary			
To further evaluate the long-term safety and tolerability of ruxolitinib cream in adolescents with AD.	Changes in vital signs, height, weight, and laboratory data for hematology and serum chemistry.		
To characterize the PK of ruxolitinib cream in adolescents with AD.	Trough concentrations of ruxolitinib at each postbaseline visit.		

Overall Design:

Table 2 presents the key study design elements. Further study details are presented after the table.

Table 2: Key Study Design Elements

Study Phase	Phase 3
Clinical Indication	Topical short-term and noncontinuous chronic treatment of mild to moderate AD in nonimmunocompromised patients 12 to 17 years of age whose disease is not adequately controlled with topical prescription therapies or when those therapies are not advisable.
Population	Male and female participants 12 to 17 years of age with a diagnosis of AD for at least 2 years, a total IGA score of 2 or 3, and BSA involvement of 3% to 20% (excluding the scalp).
Number of Participants	Approximately 100 participants will be enrolled.
Study Design	Open-label, single-group, LTS study.
Estimated Duration of Study Participation	Participants will take part in the study for up to approximately 60 weeks: 28 days in the screening period, 8 weeks in the CT period, 44 weeks in the LTS period, and 30 days in the safety follow-up period.
Data Safety Monitoring Board/Data Monitoring Committee	No
Coordinating Principal Investigator	To be determined

Treatment Groups and Duration:

[figure not shown]
This is a Phase 3, open-label, 1-year safety study of ruxolitinib cream in approximately 100 adolescents (ages \geq 12 years to < 18 years) with AD whose disease is not adequately controlled with topical prescription therapies or when those therapies are not advisable (see study design schema in Figure 1).

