2.2.1. Scientific Rationale for Study Design

As the intent of this study is to further assess the safety of ruxolitinib 1.5% cream BID in adolescents with AD in addition to what was studied in the Phase 3 studies, INCB 18424-303 and INCB 18424-304, the study population has been based on that in the Phase 3 studies, namely adolescents aged \geq 12 to < 18 years of age with AD for at least 2 years and affecting 3% to 20% BSA (excluding the scalp) plus a total IGA score of 2 or 3.

In addition, given the recent concerns about the potential thromboembolic and cancer risks of oral JAK inhibitors that are currently approved as treatments for rheumatoid arthritis (Olumiant 2021, Xeljanz 2021), the exclusion criteria have been augmented where necessary to exclude anyone with current or a history of venous thromboembolism (DVT or PE), major adverse cardiovascular events, or malignancies.

The primary and secondary objectives and endpoints focus on further assessing the safety and tolerability of ruxolitinib 1.5% cream BID in adolescents through assessment of TEAEs, vital signs (in particular height and weight), laboratory data for hematology and serum chemistry, and PK (trough concentrations of ruxolitinib).

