**Table 1: Objectives and Endpoints**

Objectives	Endpoints
Primary	
To evaluate the long-term safety and tolerability of ruxolitinib cream in adolescents with AD.	Incidence of TEAEs, assessed by monitoring the type, frequency, and severity of AEs.
Secondary	
To further evaluate the long-term safety and tolerability of ruxolitinib cream in adolescents with AD.	Changes in vital signs, height, weight, and laboratory data for hematology and serum chemistry.
To characterize the PK of ruxolitinib cream in adolescents with AD.	Trough concentrations of ruxolitinib at each postbaseline visit.
Exploratory	

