3.3.3.2	Shift Summary of Hematology Laboratory Values in CTCAE Grade - to the Worst Abnormal Value in the LTS Period	LTS-EV
3.3.4.1	Shift Summary of Chemistry Laboratory Values in CTCAE Grade - to the Worst Abnormal Value in the CT Period	FAS
3.3.4.2	Shift Summary of Chemistry Laboratory Values in CTCAE Grade - to the Worst Abnormal Value in the LTS Period	LTS-EV
3.3.5.1	Shift Summary of Hematology Values - to the Worst Abnormal Value in the CT Period	FAS
3.3.5.2	Shift Summary of Hematology Values - to the Worst Abnormal Value in the LTS Period	LTS-EV
3.3.6.1	Shift Summary of Chemistry Values - to the Worst Abnormal Value in the CT Period	FAS
3.3.6.2	Shift Summary of Chemistry Values - to the Worst Abnormal Value in the LTS Period	LTS-EV
3.4 Vital Signs		
3.4.1	Summary of Systolic Blood Pressure in the Treatment Period	FAS
3.4.2	Summary of Diastolic Blood Pressure in the Treatment Period	FAS
3.4.3	Summary of Pulse in the Treatment Period	FAS
3.4.4	Summary of Respiratory Rate in the Treatment Period	FAS
3.4.5	Summary of Body Temperature in the Treatment Period	FAS
3.4.6	Summary of Height in the Treatment Period	FAS
3.4.7	Summary of Weight in the Treatment Period	FAS

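### Height and weight are summarised only as pooled values and changes, so the planned tables give no expected growth against which to read the one-year gain

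*SAP*

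**What the plan says.** SAP Table 1 gives the secondary safety endpoint as "Changes in vital signs, height, weight, and laboratory data for hematology and serum chemistry". The design rationale in Protocol 2.2.1 singles these two measures out: "vital signs (in particular height and weight". Protocol 8.3.3 has them measured at baseline and Weeks 8, 28 and 52 (or early termination), with height as the average of three stadiometer readings.

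The planned analysis is one sentence in SAP 9.4: "Height and weight values at each scheduled visit, change, and percentage change from baseline for height and weight will be summarized descriptively". SAP 5.2 reports participants in a single total group. Appendix A lists one output for each measure, both on the FAS: Table 3.4.6, "Summary of Height in the Treatment Period", and Table 3.4.7, "Summary of Weight in the Treatment Period". Protocol 10.4.2.2 and Protocol Table 13 likewise ask only for descriptive statistics and mean change.

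Protocol Table 2 describes the design as "Open-label, single-group, LTS study". The subgroup analyses in SAP 9.2.2 (sex, race, ethnicity) apply to TEAEs, and age is not among them.

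**The concern.** Adolescents gain height and weight whether or not the drug has an effect, and the amount depends strongly on age and sex. For blood pressure or a laboratory value, a mean change near zero over a year is a natural benchmark. For height it is not, and percentage change does not help. With no control arm, the benchmark has to come from outside the trial, and the plan names none. A mean gain in cm or kg is then hard to read as either reassuring or worrying. That matters because Protocol 2.2 gives long-term safety in adolescents as the purpose and describes the study as an FDA post-marketing requirement.

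**Working it through.** **The plan's own figures.** The documents give no growth velocity, growth SD or shortfall of interest, so there is no planned growth figure to reproduce. The one probability in Protocol 10.1 concerns adverse events. It reproduces (1 − 0.95^100 = 0.994, stated as > 99%) but has no bearing here.

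**Step 1: set the parts of the endpoint side by side.**

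| Component | Planned summary | Reference in the plan |
|---|---|---|
| Hematology, chemistry | Value, change, shifts | Normal ranges and grades (SAP 9.3.2): "Shift tables will be presented showing the change in CTCAE grade from baseline to worst grade postbaseline as well" |
| Blood pressure, pulse, temperature, respiratory rate | Value, change, percentage change | Limits for two age bands (SAP Tables 4 and 5): "The abnormal values for participants exhibiting clinically notable vital sign abnormalities will be listed by age group" |
| Height, weight | Value, change, percentage change | None |

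No z-score, percentile, growth reference, or split of growth by age or sex appears in the SAP text or in the Appendix A tables, figures and listings. The sample displays and the standard table conventions are separate documents and were not available, but no Appendix A title suggests such an output.

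**Step 2: how far normal growth alone can move the pooled mean.** Assume velocities of 6, 3 and 1 cm per year for ages 12–13, 14–15 and 16–17.

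- Younger sample, mix 50/30/20%: 0.5×6 + 0.3×3 + 0.2×1 = 4.1 cm.
- Older sample, mix 20/30/50%: 0.2×6 + 0.3×3 + 0.5×1 = 2.6 cm.

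The swing between these mixes is 0.3 × (youngest-band velocity − oldest-band velocity), here 0.3×5 = 1.5 cm. For four other assumed sets:

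- 4/3/2: 0.3×2 = 0.6 cm
- 5/2/0.5: 0.3×4.5 = 1.35 cm
- 7/4/2: 0.3×5 = 1.5 cm
- 7/3/0.5: 0.3×6.5 = 1.95 cm

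This illustrates height only. The same logic applies to weight, but no figure was derived for it.

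**Step 3: what other planned outputs supply.** SAP 6.1.1 and Table 1.2 summarise age and sex for the FAS. Listing 2.4.1 covers demographics by participant. Listing 2.9.1 is titled only as vital signs, but Protocol 4.1 counts height and weight among vital signs and SAP 9.4 places them under that heading, so it probably holds them by visit. Joined, the two listings would show age by sex and who has a Week 52 height.

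**Step 4: precision of the mean gain (used under the objection).** Assume velocities 6/3/1, mix 35/35/30%, and a within-age SD of 1 to 2 cm.

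- Expected gain: 0.35×6 + 0.35×3 + 0.30×1 = 3.45 cm.
- Between-age variance: 0.35×36 + 0.35×9 + 0.30×1 − 3.45² = 4.15.
- Pooled SD: √(4.15 + 1) to √(4.15 + 4) = 2.27 to 2.85 cm. The 95% half-width at n=100 is 1.96×SD/10 = 0.44 to 0.56 cm.
- Within-age half-width: 1.96×(1 to 2)/10 = 0.20 to 0.39 cm at n=100, and 1.96×(1 to 2)/√70 = 0.23 to 0.47 cm at n=70.
- Dropout by age: if 20/30/40% leave, the remaining mix is 39.7/34.8/25.5% and the expected gain 3.68 cm. If 40/30/20% leave, it is 30.2/35.3/34.5% and 3.22 cm. The shift is 0.23 cm either way, and 0.08 to 0.30 cm over the other velocity sets and a lighter dropout pattern.

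**The case against.** **The expectation can be rebuilt.** Table 1.2 shows whether the sample is old or young, and Listings 2.4.1 and 2.9.1 together probably allow a participant-level comparison. This stands, and it is why the point concerns interpretability only. A listing still does not relate growth to expectation; someone has to do that afterwards with a reference of their own choosing.

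**The SAP delivers what the protocol asks.** Descriptive statistics are what Protocol 10.4.2.2 and Table 13 specify, and no hypothesis is tested. This also stands: there is no contradiction or departure to correct.

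**The contrast with the other measures is partial.** The vital-sign limits only drive listings of individual values, and mean changes in those measures have no external reference either. That is fair, though zero is a usable benchmark for them and not for height.

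**A stronger reading is tempting.** A reader might infer that a moderate growth shortfall, say 20% (0.2×3.45 = 0.69 cm), would be missed. The documents do not support that. Every growth rate and SD behind it is assumed. The 0.44 to 0.56 cm half-width counts between-age variance that comparison with the sample's own age mix removes; the within-age half-width is 0.20 to 0.39 cm at n=100. Adding about 0.1 to 0.3 cm linearly for imperfect adjustment gives 0.30 to 0.69 cm, so 0.69 cm sits at the top edge. Listing 2.9.1 would probably remove much of that addition by showing who was measured at Week 52.

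Nor do z-scores guarantee detection. With an assumed reference SD of 6 to 8 cm, 0.69 cm is 0.09 to 0.12 z. With an assumed SD of z-score change of 0.2 to 0.4, the half-width is 0.04 to 0.08 at n=100 and 0.05 to 0.09 at n=70. At the extreme, 0.094 exceeds 0.086.

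**Scores could be computed later.** True, since the data are collected. The reason to specify them now is to fix the reference before the results are seen.

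**Conclusion.** The point holds as a cheap improvement worth making, not as an error. The planned height and weight tables meet the wording of the endpoint but carry no expected value for a growing, mixed-age, mixed-sex sample without a control arm. Between plausible age mixes, normal growth alone moves the expected mean gain by 1.5 cm on the main assumed velocities, and by 0.6 to 1.95 cm over the other sets. Those velocities are assumptions; the absence of a reference in the plan is not. Other planned outputs soften the problem, on the reading that Listing 2.9.1 includes height and weight. No claim is made that a shortfall of any particular size would go unseen.

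**What to change.** Keep the planned summaries and add to SAP 9.4, in substance:

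> Height and weight will also be expressed as age- and sex-standardised z-scores from one growth reference, named here before analysis, at baseline and Weeks 8, 28 and 52. Mean change from baseline in z-score will be given with a 95% CI; Week 52 is the main time point. Age at each visit will be derived from the date of birth or, if only the year is held, from the 01 JUL convention of Section 4.1.4 plus elapsed time.

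Add one height and one weight z-score table after 3.4.7. Appendix A allows its lists to change without an amendment only where the nature of the analysis is unaffected, so the score and its reference belong in the text of 9.4.

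The cost is one paragraph and two tables, with no new data, visit or procedure. The limits should be stated:

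- One reference must serve a North American and European sample.
- Age may be approximate, since Protocol 8.1.5.1 records year of birth/age. An error of up to 0.5 year, at 6 cm per year and a reference SD of 8 to 6 cm (assumed), is 0.5×6/(8 to 6) = 0.38 to 0.50 z in level for one participant. It largely cancels in the change: if velocity alters by 1 to 3 cm per year for each year of age (assumed), the SD of its effect on the mean change of 100 is (1 to 3)/√12/(8 to 6)/10 = 0.004 to 0.014 z.
- Pubertal timing is not captured.
- Without a control arm, a deficit could not be attributed to the drug.
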